8.2.6 Device using specification

According to the results of random allocation, the investigators apply the study medical device to the subjects who enter the test group, and the control medical device to the subjects who enter the control group. If a subject requires the use of a circular stapler during the trial, the brand and model of the circular stapler shall be recorded.

⁹ Only the conditions related to the use of test product and control product are recorded here. However, during the trial, subjects may use circular stapler or other staplers. If adverse events related to the stapler also occur, the occurrence shall be truthfully recorded in the adverse events.

¹⁰ It is necessary to use gas injection method for inspection. If relevant examination is not required, the CRF should be completed as "Not Applicable".

¹¹ If yes, please specify the reason and whether it is related to the stapler.

¹² The model and amount used in the clinical trial shall be truthfully recorded. Meanwhile, whether the subject uses the brand and model of circular stapler shall also be collected.

¹³ Investigators faithfully record whether each reload is used laparoscopically or laparotomically.

¹⁴ The tissues cut and anastomosed by each cartridge, such as stomach, duodenum, jejunum, ileum, appendix, ascending colon, transverse colon, descending colon, sigmoid colon and rectum, etc. are recorded.

¹⁵ If corresponding symptoms occur, the reasons for confirming the event should also be briefly described, so as to facilitate the review. In addition, generally anastomotic bleeding is judged by the presence or absence of persistent fresh bleeding from the gastric tube, and the diagnosis is confirmed by gastroscopy or second surgical exploration.

8.2.7 Visit schedule

Subjects should receive 4 visits before the end of the study: before surgery (Day -7 \sim 0), during surgery (Day 0), on Day 7 \pm 2 after surgery, and on Day 30 \pm 5 after surgery.

8.2.7.1 1st visit 1/before surgery (Day -7 \sim 0)

- (1) The ICF form shall be signed;
- (2) Screening subjects according to the inclusion and exclusion criteria;
- (3) Recording demographic data, current medical history and past medical history are recorded;
- (4) Examining vital signs;
- (5) Performing preoperative imaging examination (CT examination);
- (6) Performing laboratory examinations¹⁷ (blood routine, coagulation routine, blood biochemistry, fasting blood glucose, occult blood test, cardiac ultrasound, pulmonary function, blood pregnancy test);
- (7) Recording concomitant and concomitant medications;
- (8) Recording protocol deviations;

8.2.7.2 2nd visit 2/during surgery (Day 0)

- (1) Examining vital signs;
- (2) Intraoperative observation records (intraoperative observation, observation of investigational product, use of device);
- (3) Randomization;
- (4) Use of device;
- (5) Recording concomitant medication/treatment;
- (6) Monitoring of adverse events and serious adverse events;
- (7) Recording device defects;
- (8) Recording protocol deviations;

8.2.7.3 3^{rd} visit 3/after surgery (Day 7 ± 2 days)

- (1) Examining vital signs;
- (2) Conducting laboratory examinations (blood routine, coagulation routine, blood biochemistry, occult blood test);
- (3) Conducting postoperative imaging examinations (angiography 8, upper gastrointestinal radiography 8, gastrointestinal endoscopy 8, postoperative abdominal CT);
- (4) Postoperative follow-up observation;

¹⁶ For imaging examination, reports/results within 1 month prior to surgery in our hospital my be accepted.

¹⁷ For laboratory examination, reports/results at within 7 days prior to surgery in our hospital may be accepted.

Clinical Trial on Performance and Safety of Disposable Powered Articulating Endoscopic Linear Cutter Stapler in Gastrointestinal Tissue Cutting and Anastomosis

- (5) Postoperative follow-up observation;
- (6) Recording concomitant and combined medications;
- (7) Recording adverse events and serious adverse events;
- (8) Recording protocol deviations;

8.2.7.4 4th visit/after surgery (Day 30 ± 5 days)

- (1) Examine vital signs;
- (2) Occult blood test;
- (3) Conducting postoperative imaging examinations (angiography, upper gastrointestinal radiography, gastrointestinal endoscopy) 8;
- (4) Postoperative follow-up observation (anastomotic healing time, whether there is anastomotic bleeding, whether there is anastomotic leakage, whether there is stricture and other complications);
- (5) Recording concomitant and combined medications;
- (6) Monitoring adverse events and serious adverse events;
- (7) Recording protocol deviations;

8.2.8 Concomitant medication/treatment management

If a subject takes medication or therapeutic measures that caused the AE for various reasons during the study, such situation shall be recorded in the case report form (CRF) by investigators for reference.

- (1) Prohibited therapies: Products with similar efficacy to the study medical device and the control device are prohibited for use by all subjects during the clinical trial.
- (2) Allowable treatment: The treatment with other drugs or therapeutic measures required due to underlying diseases, concomitant diseases or adverse events should be recorded in the original medical records in detail, including the name, dosage, usage of the drug and the name, usage and frequency of the therapeutic measures.
- (3) The generic name, type, dose, frequency, route of administration and days of administration of other drugs used by the subjects as well as the name, method and frequency of treatment should be recorded in detail. The information is used to evaluate the possible bias on clinical trial results.

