8.1.15 Effectiveness evaluation method

8.1.15.1 Main effectiveness evaluation indicators, method and time for evaluation, recording and analysis

(1) Success rate of anastomosis

Justification for selection: According to the *Guidelines for Technical Review of Endoscopic Stapler Registration* issued by NMPA (original CFDA) on March 13, 2017, the "success rate of anastomosis" is selected as the primary evaluation indicator for such products.

Evaluation time: During the surgery.

Evaluation site: Tissues receiving linear stapler for gastrointestinal anastomosis.

Evaluation method: The transection and anastomosis of lung tissues are performed during the operation. The device is withdrawn after successful triggering. The cutting staple line is carefully checked for integrity, air leakage and bleeding. Anastomosis is considered as successful if all anastomotic rings are intact without leakage or bleeding, otherwise it is considered as failure. If necessary, the gas injection method is used to inspect whether there is bubble overflow at anastomotic stoma. If there is no bubble overflow, it is recorded as successful anastomosis; if there is obvious bubble overflow, it is recorded as anastomosis failure.

Formula: Anastomosis success rate = number of subjects with successful anastomosis in each group/total number of subjects in this group \times 100%

Precautions: During gastrointestinal tissue cutting and anastomosis, the subject may be converted into thoracotomy due to his complicated condition. At this time, the investigators need to determine whether the subject's conversion to thoracotomy is caused by the stapler. If it is caused by the stapler, it is judged as anastomosis failure. After gastrointestinal tissue anastomosis, the investigator may need to supplement the stitching treatment for anastomotic tissues. If the supplement is resulted from incomplete anastomosis ring, leakage and bleeding, it is considered as anastomosis failure.

8.1.15.2 Secondary effectiveness evaluation indicators, method and time for evaluation, recording and analysis

(1) Stapler-resulted conversion rate

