8.1.17 Operational performance evaluation

(1) Stapler operating performance evaluation

Measurement time: During the stapler operation process.

Evaluation method: ① Whether the single-handed operation of stapler is smooth; ② whether the stapler can fire normally; ③ whether the back-off is smooth after the completion of anastomosis, whether there is tissue entrapment, whether there is resistance; ④ whether the stapler can fire continuously for many times is reliable; ⑤ whether the stapler can completely cut off the tissue; ⑥ whether the battery supply is stable; ⑦ whether the electric cutting is smooth.

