- (2) Observation of the study product⁹: whether the digestive tract is successfully transected and stapled, whether the cutting anastomosis ring/staple line is complete, whether there is leakage of cutting anastomosis ring/staple line, whether there is bleeding of cutting anastomosis ring/staple line, whether there is bubble overflow at the anastomotic stoma¹⁰, whether there are indicators of conversion to laparotomy¹¹, number of needles for anastomotic repair¹¹, whether there is anastomotic dehiscence¹¹, whether there are other complications¹¹, whether the staple line or tissue buttressing materials are used, and the operating performance of stapler;
- (3) Device use¹²: model and specification of electric stapler, model of cartridge, use condition¹³, cutting and stapling tissues¹⁴, device defects;
- (4) Postoperative follow-up observation: first anus exhaust time, semi-liquid feeding time, first defecation time, bowel sound recovery time, whether there is anastomotic bleeding¹⁵, whether there is anastomotic leakage¹⁵, whether there is anastomotic stenosis¹⁵, whether there are other complications¹⁵, whether there is abdominal effusion and the abdominal effusion volume;
- (5) Routine observation items: adverse events, concomitant medication, protocol deviations.

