9.4 Expected Dropout Rate

A 20% dropout rate is expected during sample size estimation.

This drop-out rate refers to the proportion of subjects who finally can not be included in the primary analysis. Drop-out subjects refer to those confirmed by the principal investigator with serious protocol violation (affecting the main evaluation/efficacy evaluation). The following conditions may be included, but not limited to: the subject violates the inclusion and exclusion criteria; the subject does not receive any examination/treatment with the study device; the subject receives the concomitant medication/device prohibited by the protocol; the data of main evaluation indicators are missing; the subject fails to obtain any data after randomization; the subject fails to complete the follow-up visit according to the regulations.

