9.9 Selection Criteria and Reasons for Subjects Included in Analysis

- (1) Full analysis set (FAS): According to the basic principles of intention to treat analysis, all the subjects who have received at least one treatment with the investigational medical device and had at least one post-baseline observation data are included in the FAS. The FAS will be used as the primary population for baseline data (and efficacy evaluation) in this study.
- (2) Per-protocol set (PPS): It refers to the subjects in the FAS who do not seriously deviate from the trial protocol, have good compliance and have no missing primary efficacy indicators. The PPS will be used as the primary population for efficacy analysis in this study.
- (3) Safety set (SS): All subjects who have received at least one treatment with the investigational medical device and had at least one safety evaluation. The SS will be used as the primary population for safety analysis in this study.

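### A subject whose assigned stapler fails and is rescued with another linear cutter can be left out of the PPS, because sections 8.2.8(1), 9.4 and 9.9 contain no rescue exception

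*Combined protocol and SAP*

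**What the plan says.** **The ban.** Section 8.2.8(1): "Products with similar efficacy to the study medical device and the control device are prohibited for use by all subjects during the clinical trial". No exception follows for rescue after failure of the assigned stapler.

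**The exclusion ground.** Section 9.4 counts as drop-outs the subjects who cannot enter the primary analysis. "Drop-out subjects refer to those confirmed by the principal investigator with serious protocol violation (affecting the main evaluation/efficacy evaluation", it says, and its open-ended list of conditions that may qualify includes this one: "the subject receives the concomitant medication/device prohibited by the protocol". Section 8.1.3(4) states that investigators know the allocation.

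**The analysis sets.** Section 9.9 restricts the PPS to FAS subjects without serious deviation, with good compliance and with a primary result. It adds: "The PPS will be used as the primary population for efficacy analysis in this study". The same section also gives the FAS a primary role for efficacy evaluation.

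**The endpoint.** Section 8.1.15.1: "Anastomosis is considered as successful if all anastomotic rings are intact without leakage or bleeding, otherwise it is considered as failure". The denominator is all subjects in the group.

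**Text pointing the other way.** Section 8.1.5 and footnote 9 (to 8.2.5.5) accept that circular or other (types of) staplers may be used, and ask only that this be recorded. Section 8.2.8(2) permits treatment needed for adverse events, without mentioning a second stapler.

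**The concern.** Another linear cutter is the plainest example of a product with efficacy similar to the two trial devices. The subjects most likely to need one during surgery are those in whom the assigned stapler has just failed. Use of the prohibited product is then a consequence of the primary outcome, and excluding for it means excluding on the outcome.

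The direction matters in a non-inferiority trial. Removing a test-arm failure raises the observed test success rate and moves the lower confidence limit away from -10%. The decision is made after the outcome is known, by someone who knows the arm. Section 9.7.2 adds discussion with the biostatistician, and section 10.4 settles the analysis sets before lock, but neither says that this review is blind to arm or outcome.

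**Working it through.** **Inputs.** From section 9.2: success 97% in both arms, margin 10 points, one-sided alpha 0.025, power 80%, 65 per arm raised to 82 (164 in total). From section 9.5: success if the lower 95% limit of the difference exceeds -10%. The protocol names no interval method, so I ran the Miettinen-Nurminen score interval and the Wald interval. The documents give no rate of rescue with another linear cutter; removal rates below are assumptions.

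**1. The plan's own figures reproduce.**
- n = 2 × 0.97 × 0.03 × (0.8416 + 1.9600)² / 0.10² = 45.68, so 46.
- Stated correction: (46/4) × (1 + √(1 + 4/(0.10 × 46)))² = 64.4, so 65.
- Dropout: 65/0.8 = 81.25, so 82 per arm and 164 in total.
- Expected failures at 97%: 82 × 0.03 = 2.46 per arm. With so few, one classification can count.

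**2. Effect of one exclusion at the boundary.** Wald lower limit = p₁ − p₂ − 1.96 √(p₁(1−p₁)/n₁ + p₂(1−p₂)/n₂). For 76/82 v 80/82 this is −0.0488 − 1.96 × 0.0334 = −0.1143. The score limit is found by inverting the score test.

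| Test v control | Score lower limit | Wald lower limit |
|---|---|---|
| 77/82 v 80/82 | -11.42% (fails) | -9.82% (passes) |
| 77/81 v 80/82, one test failure removed | -9.94% (passes) | |
| 76/82 v 80/82 | | -11.43% (fails) |
| 76/81 v 80/82, one test failure removed | | -9.95% (passes) |

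The flip occurs under both intervals, one failure later under Wald.

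**3. How often a result sits exactly there.** Exact binomial enumeration, 82 per arm, control 97%. Probability that the full result fails but passes with one test-arm failure removed:

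| True test success | Score | Wald |
|---|---|---|
| 87% | 2.1% | 4.4% |
| 92% | 12.4% | 15.4% |
| 97% | 7.9% | 3.2% |

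**4. Average effect on type I error.** True rates 87% v 97%, each failure removed independently with probability f in both arms, score interval:

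| f (assumed) | P(declare non-inferiority) |
|---|---|
| 0 | 2.1% |
| 5% | 2.6% |
| 10% | 3.2% |

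By Wald the figure is 4.3% at f = 0 and 6.7% at f = 10%.

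**5. A ceiling for one removal.** If one test-arm failure were removed every time, and none from the control arm, score type I error would be 0.0214 + 0.0215 = 0.0429, or 4.3%.

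**The case against.** **Exclusion is not automatic.** A reader might infer that every rescued failure leaves the PPS. The text does not say that. Section 9.4 lists conditions that may qualify and requires a serious violation affecting the main evaluation. If the assigned device's line has already been scored a failure, later rescue cannot change that score, so excluding the subject would strain the wording. Section 8.1.5 and footnote 9 also accept other staplers. These points stand, and they make exclusion a permitted reading rather than a required one. They do not close the route: other types of stapler need not include a competing linear cutter, and neither place addresses membership of an analysis set.

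**The misfire is scored.** A reader might infer from "The device is withdrawn after successful triggering" that a misfire leaving no line has no score under 8.1.15.1. The documents do not support this. Without a line there is no intact ring, so the case falls under the clause that makes everything else a failure, and the subject stays in the all-subjects denominator. Firing and stapling are also recorded ("whether the stapler can fire normally" in 8.1.17, "whether the digestive tract is successfully transected and stapled" in 8.2.5.5). What stays open is only how an intact line later made by a substitute stapler is scored.

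**The FAS keeps these subjects.** True. But 9.9 gives both sets a primary role for efficacy, so a favourable PPS result would not clearly be overruled.

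**A separate SAP may settle it.** Section 9.1 defers the methods to a SAP finalised before lock, and its text is not among the documents. The absence of a rule is established for the protocol only.

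**Conclusion.** The point holds as a minor one. Sections 8.2.8(1), 9.4 and 9.9 together permit a failure rescued with another linear cutter to leave the set named primary for efficacy, and nothing in the protocol requires it to stay as a failure. On average the effect is small: score type I error at the margin goes from 2.1% to 2.6-3.2% if 5-10% of failures are removed in both arms. The 4.3% ceiling assumes removal of a test-arm failure every time and should not be read as a forecast. The practical exposure is a result close to the margin, where one classification can change the conclusion. All of this depends on an assumed removal rate, on 82 evaluable subjects per arm, and on an interval method that the protocol does not name.

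**What to change.** In 9.4 and in the PPS definition in 9.9, state that use of another stapler to rescue a failure of the assigned device is not a ground for exclusion. State also that the subject stays in both FAS and PPS as an anastomosis failure, even if the substitute's line is intact. Elective switching to a competing linear cutter remains a deviation. Carry the same rule into the SAP.

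Two further edits are optional clarifications: a sentence in 8.1.15.1 that a misfire requiring another stapler is a failure, and a clause in 8.2.8(1) exempting the staplers permitted by 8.1.5 and 8.1.5.1.

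The cost is a few sentences; 65, 82 and 164 are unchanged. The downsides are that a few mixed-device subjects stay in the PPS and that observed success may be slightly lower in either arm.

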8.2.9 Case report form completion

Case Report Form (CRF) is a document designed according to the clinical protocol to record the data of each subject during the trial. The correct completion of case report form will help to make a correct judgment on the trial results. Each investigator should complete the case report form carefully and pay attention to the following points:

(1) Required fields on the CRF must not be left blank;

- (2) When completing the CRF, be sure to make the unit of test results consistent with the unit filled in;
- (3) All data on the CRF should be derived from original documents and be consistent with the original documents;
- (4) The investigator should complete and sign the CRF within 2 weeks after each subject completes relevant examinations, which is for overall monitoring by the clinical research associate;
- (5) If there is any uncertainty in the filling process, please communicate with the sponsor in a timely manner.

8.3 Monitoring Plan

The sponsor shall, in accordance with the requirements of *Good Clinical Practice for Medical Devices*, select the qualified monitor to perform monitoring responsibilities for all the participating institutions. The monitoring frequency of each participating institution will be adjusted according to the speed of subject recruitment and subject number in each institution participating in the study. The monitor will complete the following responsibilities:

- (1) Confirming that the clinical trial institution has been equipped with appropriate conditions before the trial, including qualified staffing and training, complete laboratory equipment, good working condition, expected to have a sufficient number of subjects, and investigators familiar with the trial requirements;
- (2) Monitoring whether the clinical trial institutions and investigators abide by relevant regulations, this specification and clinical trial protocol before, during and after the trial;
- (3) Confirming that each subject has signed the ICF before participating in the clinical trial, and that the inclusion of subjects as well as the progress of the trial are well known; monitoring and recording the failure follow up, non-conducted trial, non-conducted examination by the investigators, and whether the errors and omissions are corrected; for the revised ICF, confirming that the clinical trial process is not completed and the affected subjects have re-signed the ICF;
- (4) Confirming that all the CRFs are correctly filled in and consistent with the original data; that all the errors or omissions have been corrected or explained, which have been signed and dated by the investigators; and that the disease type, total number of cases and gender, age and therapeutic effect in each trial have been confirmed and recorded;
- (5) Confirming that the subject withdrawing from the clinical trial or non-compliant with the requirements set forth in the ICF is recorded and discussed with the investigators;
- (6) Confirming that all adverse events, complications and other device defects are recorded, and serious adverse events and device defects that may cause serious adverse events are reported and recorded within the specified time;
- (7) Monitoring the supply, use, maintenance, transportation, reception, storage, distribution, processing and recovery of investigational medical device samples;

- (8) Supervising the regular maintenance and calibration of relevant equipment during the clinical trial;
- (9) Ensuring that all the documents related to the clinical trial received by the investigators are of the latest version;
- (10) Submitting a written report to the sponsor after each monitoring, which shall include the name of the monitor, date of monitoring, time of monitoring, place of monitoring, content of monitoring, name of the investigator, completion status of the project, existing problems, conclusions, and corrections to errors and omissions, etc.

9. Statistical Considerations

9.1 Statistical Design, Methods and Analysis Procedure

This study is a prospective, multi-center, stratified block randomization, incomplete blinding, parallel positive control and non-inferiority test. All statistical analysis methods are detailed in the statistical analysis plan. The first draft of the statistical analysis plan will be formed after the trial protocol and case report forms are finalized and will be finalized before database lock.

